2.2 Analysis sets

The Screened Set (SCR) includes all participants who provided study informed consent.

The Randomized Set (RAN) consists of all participants who received a randomization number, regardless of whether double blind treatment received or not.

The Full Analysis Set (FAS) consists of all randomized participants with the exception of those mis-randomized participants who did not receive study drug. Mis-randomized participants are defined as not qualified for randomization and were inadvertently randomized into the study. According to the intent to treat principle, participants will be analyzed according to the treatment they have been assigned to during the randomization procedure. The FAS will be used in analyses for the primary, secondary, and the study objectives in Part 1.

The Safety Set (SAF) includes all participants who received at least one dose of study treatment. Participants will be analyzed according to the study treatment received. This will be the primary population for the safety analyses in Part 1.

Novartis	For business use only	Page 20
SAP amendment 4		CKJX839C12301

Note that the Safety Set allows the inclusion of non-randomized participants who receive double-blind treatment in error.

The Open-label Phase Analysis Set (OAS) includes all participants who entered study Part 2 and received at least one dose of study drug in Part 2. The OAS will be used to analyze the data from participants who entered Part 2.

Note that in Part 1 the number of participants in FAS equals the number of participants in SAF, so only one open-label phase analysis set is defined for Part 2.

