4.2 Rationale for dose/regimen and duration of treatment

The established dose regimen for inclisiran for adults is 300 mg s.c. on Day 1, Day 90 and every 6 months thereafter. Based on nonclinical and clinical data, including phase I, II and III clinical studies as well as pharmacodynamic (PD) modeling in adult participants, the same dose and dose regimen will also be used in the present study in adolescents.

In adult participants, maximum reductions in LDL-C and PCSK9 levels with inclisiran were achieved with single s.c. doses of 300 mg inclisiran sodium, with no additional meaningful benefit observed at higher doses. Three large pivotal phase III studies in adult participants with ASCVD, ASCVD risk equivalents, and/or HeFH demonstrated that the dose regimen used in the present study (300 mg inclisiran sodium s.c. on Day 1, Day 90 and every 6 months thereafter) resulted in placebo-adjusted percentage reductions in LDL-C from baseline at Day 510 of 48% to 52%, with time-adjusted average reductions of 44% to 54% sustained over 18 months. This dose and regimen also showed good tolerability of inclisiran, with a safety profile similar to placebo, except for a higher incidence of AEs at the injection site with inclisiran. No patient populations were identified that required an inclisiran dose adjustment. Doses up to 900 mg (3-fold therapeutic dose) were studied which was safe and well tolerated in healthy adult subjects.

Adult data has shown that the plasma PK of inclisiran does not predict PD effects. Inclisiran is rapidly cleared from plasma in 24 to 48 hours depending on the dose level, yet because of its site and mechanism of action, its LDL-C lowering effect is measurable for more than 6 months even after a single dose, the basis of the 6-monthly dosing interval. Inclisiran is delivered to hepatocytes due to its conjugated structure with GalNAc and stored intracellularly in RISC complexes, where target protein suppression occurs for months, resulting in the disconnect

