Women of child bearing potential and her parent(s)/legal representative(s) must be informed that taking the study treatment may involve unknown risks to the fetus if pregnancy were to occur during the study and agree that in order to participate in the study they must adhere to the contraception requirements.

A copy of the approved version of all consent/assent forms must be provided to Novartis after IRB/IEC approval.

8 Visit schedule and assessments

The Assessment Schedule (Table 8-1) lists all of the assessments when they are performed. All data obtained from these assessments must be supported in the participant's source documentation.

Participants should be seen for all visits/assessments as outlined in the Assessment Schedule or as close to the designated day/time as possible. Missed or rescheduled visits should not lead to automatic discontinuation.

Participants who prematurely and permanently discontinue from study treatment will continue to be followed up in the study according to the Assessment Schedule unless informed consent is withdrawn.

Participants who prematurely discontinue the study for any reason [e.g. if a participant's parent(s)/legal representative(s) / a participant (if applicable) decide to prematurely and permanently discontinue the participant from study treatment and decline further follow-up visits] should be scheduled for an EOS visit as soon as possible. At this final visit, AEs and concomitant medications should be recorded in the corresponding eCRFs.

Participants will have to comply with the following restrictions:

- Participants should have fasted for at least 8 hours for all visits for fasting lipids/lipoproteins/PCSK9 and glucose blood samples (if the participant has not fasted, the collection of laboratory evaluations must be rescheduled)
- Participants must refrain from unaccustomed strenuous physical exercise for 48 hours before the screening and any study visit until the follow-up has been completed
- Blood donation will not be allowed at any time during the study

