12.1 Analysis sets

The Full Analysis Set (FAS) comprises of all randomized participants with the exception of those mis-randomized participants who did not receive study drug. Mis-randomized participants are defined as not qualified for randomization and are inadvertently randomized into the study. According to the intent to treat principle, participants will be analyzed according to the treatment they have been assigned to during the randomization procedure. The FAS will be used in analyses for the primary, secondary,

The Safety Set includes all participants who received at least one dose of study treatment. Participants will be analyzed according to the study treatment received. This will be the primary population for the safety analyses.

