12.5.2 Safety endpoints

For all safety analyses, the safety set will be used. All tables will be presented by treatment group.

Safety summaries (tables, figures) include only treatment emergent events (events started after the first dose of study medication or events present prior to start of double-blind treatment but increased in severity based on preferred term) with the exception of baseline data which will also be summarized where appropriate (e.g. change from baseline summaries). In addition, a separate summary for deaths including on treatment and post treatment deaths will be provided. In particular, summary tables for adverse events (AEs) will summarize only treatment emergent AEs.

Adverse events

The number (and percentage) of participants with treatment emergent adverse events in Part 1 and Part 2 will be summarized in the following ways:

- by treatment, primary system organ class and preferred term alphabetically.
- by treatment, primary system organ class, preferred term alphabetically and maximum severity.

- by treatment, primary system organ class and preferred term alphabetically for treatment emergent AEs leading to study drug discontinuation.
- by treatment, primary system organ class and preferred term alphabetically for treatment emergent AEs related to study drug.

The number (and percentage) of participants with treatment emergent serious adverse events in Part 1 and Part 2 will be summarized in the following ways:

- by treatment, primary system organ class and preferred term alphabetically.
- by treatment, primary system organ class and preferred term alphabetically for treatment emergent serious AEs related to study drug.

A separate summary will be provided for adverse events leading to death.

The number (and proportion) of participants with adverse events of special interest will be summarized by treatment. Categories of AEs used in this analysis will be specified in the SAP.

A participant with multiple adverse events within a primary system organ class is only counted once towards the total of the primary system organ class.

Vital signs

All vital signs data will be listed by treatment group, participant, and visit/time and if ranges are available, abnormalities (and relevant orthostatic changes) will be flagged. Summary statistics will be provided by treatment and visit/time.

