2.8 Safety analyses

In general, for Part 1 safety analyses, the SAF will be used; for Part 2 safety analysis, the OAS will be used.

Safety summaries will include only treatment emergent adverse events (TEAEs) by Part. For Part 1, TEAEs are defined as adverse events (AEs) starting on or after the first dose of doubleblind treatment or AEs that were present prior to start of double-blind treatment but increased in severity in Part 1. For Part 2, TEAEs are defined as AEs starting after the Day 360 dosing time or AEs that were present prior to the Day 360 dosing time but increased in severity in Part 2. For Part 1, if the AE start date is the same as the date of the first dose of double-blind treatment but the time is not available for comparison, the AE will be considered as treatment but the time is not available for comparison, the AE will be considered as treatment but the time is not available for comparison, the AE will be considered as treatment but the time is not available for comparison, the AE will be considered as treatment but the time is not available for comparison, the AE will be considered as treatment but the time is not available for comparison.

Vital signs values that have complete data and time values will be assigned to pre- or post-dose assessment (as per protocol) based on the actual date/time. For values with missing date/time, the scheduled visit date and time will be used. This rule will be applied to data from scheduled visits only. If a measurement scheduled as pre-dose is actually performed post-dose, or vice versa, the data will not be used for visit/time point summary.

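### Part 2 safety tables leave out participants who stopped study drug in Part 1 but remain in follow-up, so their findings after Day 360 enter neither Part's summaries

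*SAP*

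**What the plan says.** **Protocol.** Section 12.1 defines the population by exposure at any time: "The Safety Set includes all participants who received at least one dose of study treatment". Section 12.5.2 then states: "For all safety analyses, the safety set will be used". It asks for adverse event (AE) and serious adverse event (SAE) summaries in both Parts, and for laboratory shift and clinically significant value tables for Part 1 and overall. Under section 8, participants who permanently stop study drug "will continue to be followed up in the study according to the Assessment Schedule unless informed consent is withdrawn". Section 9.1.1 repeats this, and the schedule ends at Day 720. Safety up to Day 720 is a stated secondary objective (Table 2-1).

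**SAP.** Section 2.2 narrows the role of the Safety Set: "This will be the primary population for the safety analyses in Part 1". It introduces the OAS, which "includes all participants who entered study Part 2 and received at least one dose of study drug in Part 2". Section 2.8 says: "In general, for Part 1 safety analyses, the SAF will be used; for Part 2 safety analysis, the OAS will be used". Appendix 5.3 repeats this split for AEs, diabetes assessment, laboratory data and vital signs. It plans combined Part 1 and Part 2 output only for exposure and selected efficacy parameters. Section 2.1 makes each participant's Day 360 visit the Part 1 cut-off. Where dosing time cannot separate the Parts, it assigns everything from the day after that visit to Part 2.

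**The concern.** The two documents define the post-Day-360 safety population differently, and the SAP's version leaves a gap. A participant who stops in Part 1, is not dosed again and keeps attending visits produces safety data that the protocol requires. Those data come too late for the Part 1 tables, and the participant is not in the set used for the Part 2 tables.

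Protocol 9.1.1 mandates stopping for several safety reasons, including transaminase, bilirubin and creatine kinase criteria, severe injection site reactions and anaphylaxis. Membership of the Part 2 set therefore depends on something that can be related to safety, so the omission is potentially informative. Drug effect also outlasts dosing: Protocol 4.2 says of inclisiran that "its LDL-C lowering effect is measurable for more than 6 months even after a single dose". At stake is whether the long-term safety summaries in adolescents cover everyone whom the protocol keeps under observation.

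**Working it through.** The documents state no figure for this point, so there is none to reproduce. The check traces where the data go, then applies day arithmetic.

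**1. Who is affected.** The OAS needs only one dose of study drug in Part 2. For the inclisiran arm the Day 360 placebo injection counts. A participant is outside the OAS only if all three Part 2 injections (Days 360, 450, 630) are missed. This applies to both arms.

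**2. Where that participant's data after Day 360 go.**

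| Output | Set or cut | Included? |
|---|---|---|
| Part 1 safety tables | Safety Set, cut at Day 360 visit | No, too late |
| Part 2 AE, laboratory, liver, diabetes and vital sign tables | OAS | No, not in the set |
| Combined AE or laboratory table | None planned in Appendix 5.3 | No |
| Listings (SAP 2.8.1 to 2.8.3) | All AEs, SAEs, deaths, laboratory data | Yes |
| Registry AE tables (SAP 2.8.1) | Safety Set, after study completion | SAEs, and non-serious AEs above a threshold not yet set |

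No summary table carries the laboratory, liver-test or diabetes assessment results.

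**3. The set does not follow active exposure.** Take two inclisiran participants last given active drug on Day 270. One receives the Day 360 placebo and then stops, and is in the OAS. The other stops on Day 330 and is not. Their active exposure is the same.

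**4. Exposure window.** SAP 2.4.1 defines duration of exposure as the smaller of (last dose − first dose + 180 + 1) and (last known visit − first dose + 1). With the first dose on Day 1 and follow-up continuing:

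- Last dose Day 1: 1 − 1 + 180 + 1 = 181, so the window ends on Day 181.
- Last dose Day 90: 90 − 1 + 180 + 1 = 270, so it ends on Day 270.
- Last dose Day 270: 270 − 1 + 180 + 1 = 450, so it ends on Day 450, which is 450 − 360 = 90 days past the cut-off.

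Only a last dose on Day 270 leaves exposure-window time outside the tables.

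**5. Size.** SAP 1.1 gives 141 enrolled; an exact 2:1 split gives 2/3 × 141 = 94 on inclisiran. The documents give no stopping rate. As an assumption, let 2% to 6% of 94 (1.9 to 5.6, about 2 to 6 people) stop in Part 1, miss all Part 2 doses and stay to Day 720.

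- Follow-up untabulated: 720 − 360 = 360 days each. 2 × 360/365.25 = 2.0 and 6 × 360/365.25 = 5.9 patient-years.
- Of this, within the exposure window at most: 2 × 90/365.25 = 0.5 and 6 × 90/365.25 = 1.5 patient-years, and only if every one of them was last dosed on Day 270.

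Placebo participants who stop would add to the first figure. The true number may be zero.

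**6. A second gap in the same rule.** SAP 2.8 starts Part 2 treatment-emergent AEs at the Day 360 dosing time. Participants who were not dosed that day have no such time, so changing the set alone would leave their Part 2 events unclassified.

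**The case against.** The case against giving this much weight is substantial, and most of it stands.

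- **The event that led to stopping is counted.** An AE or liver-test rise that ends treatment before Day 360 is Part 1 data and is tabulated on the Safety Set, including in the table of AEs leading to discontinuation. Only new or worsened findings after Day 360 are missed.
- **The direction is not established.** A reader might infer that removing early stoppers flatters inclisiran. The documents do not show this: event-free participants who are off drug leave the denominators too, and both arms are affected.
- **The group is narrow.** Protocol 9.1.1 allows restart and encourages it where the investigator judges it appropriate. One Part 2 injection, even the Day 360 placebo, brings a participant into the OAS.
- **Nothing is lost from the record.** Listings hold the data, and the registry table of SAEs uses the Safety Set. The SAP 2.2.1 subgroup AE tables are also specified on the Safety Set without a stated Part limit, though whether they extend to Part 2 is not said.
- **Nondeclaration cannot be claimed.** A reader might call this an undeclared departure from the protocol. SAP section 4, on changes to protocol-specified analyses, shows no text in the public copy and may be blacked out.

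Two other replies do not close the gap. SAP 2.8 qualifies its rule as general, but gives no exception for this group. The note in SAP 2.2 that the full analysis and safety sets are equal in number in Part 1 explains why there is one open-label set, not why undosed participants fall outside it.

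**Conclusion.** The point holds as a gap in the summary tables, not as a loss of data. As written, the SAP leaves required safety data after Day 360 out of both Parts' tables for any participant who stopped in Part 1, received no Part 2 injection and stayed in follow-up. This differs from Protocol 12.1 and 12.5.2. The lack of an overall laboratory table also departs from what 12.5.2 asks for.

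The size is probably small and cannot be fixed from the documents. On the assumption of 2 to 6 inclisiran stoppers followed to Day 720, about 2 to 6 patient-years are untabulated. It would be wrong to read all of that as on-drug time: under the SAP's own formula at most about 0.5 to 1.5 patient-years qualify, and only for last doses on Day 270. The omission could be informative, but no bias in either direction has been demonstrated. It is worth correcting because long-term safety is a stated objective and the remedy is simple.

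**What to change.** 1. Keep the OAS tables in SAP 2.8 as the on-treatment version.
2. Beside them, add AE, laboratory, liver and diabetes tables on the Safety Set for all participants with follow-up after Day 360. Alternatively, add overall Part 1 plus Part 2 Safety Set tables, which the protocol already requests for laboratory data. Present them by randomized sequence, footnote the number not dosed in Part 2, and show participants who stopped after placebo only as a separate group, so that no member of the Safety Set is dropped.
3. For participants with no Day 360 dosing time, start Part 2 and its treatment-emergent definition on the day after the Day 360 visit, in line with the fallback rule in SAP 2.1. State which date applies if that visit was missed.
4. Amend SAP 2.2 and Appendix 5.3 to match. If no participant qualifies, one footnote saying so is enough.

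The cost is SAP wording, one date rule and a few extra tables from existing data. The downside is that a few off-drug participants enter the added denominators, which is why the OAS tables stay alongside.

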2.2.1 Subgroup of interest

Subgroup analyses of primary efficacy endpoint and key secondary efficacy endpoints will be performed on the FAS only.

Number	Subgroup	Categories			
1	Gender	Male	Female		
2	Age-group	≥ 12 - < 15	≥ 15 - < 18		
3	Race	White	Black	Asian	Other
4	Ethnicity	Hispanic or latino	Not Hispanic or latino	Other**	
5	Body mass index	<= median	> median		
6	Study center region*	North America	Europe	Other	
7	Baseline statin use	Yes	No		
8	Baseline LDL-C	<= median	> median		
9	Baseline PCSK9	<= median	> median		

 Table 2-2
 Sub-group for efficacy analysis

*Region:

North America: Canada, United States;

Europe: Czech Republic, France, Germany, Greece, Hungary, Italy, Netherlands, Norway, Poland, Russian Federation, Slovakia, Slovenia, Spain, Switzerland, Israel, Turkey, United Kingdom;

Other: Taiwan, South Africa, Malaysia, Lebanon, Jordan, Brazil, Argentina. **Other: Not reported and Unknown

Subgroup analyses of all treatment emergent adverse events (TEAE) including TEAE at injection site will be displayed by treatment, SOC, and PT. The number (and percentage) of

Novartis	For business use only	Page 21
SAP amendment 4		CKJX839C12301

participants with TEAEs will be provided for each category of sub-group. The following subgroup analyses will be performed on Safety Set.

Table 2-3	Sub-group for safety	/ analysis

Number	Subgroup	Categories			
1	Gender	Male	Female		
2	Age-group	≥ 12 - < 15	≥ 15 - < 18		
3	Race	White	Black	Asian	Other
4	Body mass index	<= median	> median		

2.3 Disposition, demographics and other baseline characteristics

2.3.1 Disposition

The overall number of participants who entered, completed, and discontinued the study will be summarized and listed, including the reasons for discontinuation for each period: screening, Study Part 1, Study Part 2. The screening disposition will be based on SCR. The RAN will be used for the summary and listing of patient disposition for Study Part 1 and 2.

The number of participants in the FAS will be summarized by country, center, and treatment group for Part 1 analysis.

Number of participants with protocol deviations will be tabulated by category (e.g., selection criteria not met, subject not withdrawn as per protocol, treatment deviation, prohibited concomitant medication, other), deviation and Part. Listing of participants with protocol deviation will be provided.

The number of participants included in each analysis set will be tabulated using SCR.

2.3.2 Demographics and other baseline characteristics

Demographic and other baseline data including age, race, gender, ethnicity, country, region (North America, Europe, Other), baseline characteristics such as body height, weight, BMI, waist circumference, smoking status, number of pack years, alcohol history; baseline disease characteristics including HeFH underlying genetic mutation(s), LDL-C, TC (total cholesterol), TG (triglycerides), PCSK9, baseline use of statins or other lipid-modifying therapies (yes, no), status of statin intolerance, baseline diabetes status as determined by fasting plasma glucose and HbA_{1C}, baseline kidney function based on eGFR, baseline measurements of SBP, DBP, and pulse, will be summarized descriptively by treatment group. Listings will also be provided.

Categorical data will be presented as frequencies and percentages by treatment group. For continuous data, non-missing observations, mean, standard deviation, median, 1st and 3rd quartile, minimum, and maximum will be presented. For Part 1 analysis, these data will be summarized using RAN.

No inferential statistics will be provided for baseline comparability among the treatment groups.

Novartis	For business use only	Page 22
SAP amendment 4		CKJX839C12301

2.3.3 Medical history/current medical condition

Medical history will be coded with the Medical Dictionary for Regulatory Activities terminology (MedDRA) using the most recent version at the time of database lock. Medical history/conditions will be summarized by primary system organ class, preferred term, and treatment group. Pre-specified solicited events selected Familial Hypercholesterolemia History and other targeted family history will be summarized separately by treatment.

For Part 1 analysis, this data will be summarized using RAN.

2.4 Treatments (study treatment, prior and concomitant therapies)

In general, all summaries of treatments of Part 1 will be performed on the SAF, and All summaries of treatments of Part 2 will be performed on the OAS.

